12.2.1 Definitions

12.2.1.1 Evaluable for objective response: Patients who exhibit objective disease progression prior to the end of cycle 1 will be considered evaluable for response. For all other patients, only those patients who have measurable disease present at baseline, have received at least one cycle of therapy, and have had their disease re-evaluated will be considered evaluable for response.

12.2.1.2 Evaluable Non-Target Disease Response: Patients who have lesions present at baseline that are evaluable but do not meet the definitions of measurable disease, have received at least one cycle of therapy, and have had their disease re-evaluated will be considered evaluable for non-target disease. The response assessment is based on the presence, absence, or unequivocal progression of the lesions.

12.2.2 Disease Parameters

12.2.2.1 Measurable disease: Measurable lesions are defined as those that can be accurately measured in at least one dimension (longest diameter to be recorded) as ≥ 20 mm by chest x-ray, as ≥ 10 mm with CT scan, or ≥ 10 mm with calipers by clinical exam. All tumor measurements must be recorded in millimeters (or decimal fractions of centimeters).

Note: Tumor lesions that are situated in a previously irradiated area might or might not be considered measurable. If the investigator thinks it appropriate to include them, the conditions under which such lesions should be considered must be defined in the protocol.

12.2.2.2 **Malignant lymph nodes:** To be considered pathologically enlarged and measurable, a lymph node must be ≥ 15 mm in short axis when assessed by CT scan (CT scan slice thickness no greater than 5 mm). At baseline and in follow-up, only the short axis will be measured and followed.

12.2.2.3 **Non-measurable disease:** All other lesions (or sites of disease), including small lesions (longest diameter < 10 mm or pathological lymph nodes with ≥ 10 to < 15 mm short axis), are considered non-measurable disease. Bone lesions, leptomeningeal disease, ascites, pleural/pericardial effusions, lymphangitis cutis/pulmonitis, inflammatory breast disease, and abdominal masses (not followed by CT or MRI), are considered as non-measurable.

Note: Cystic lesions that meet the criteria for radiographically defined simple cysts should not be considered as malignant lesions (neither measurable nor non-measurable) since they are, by definition, simple cysts. 'Cystic lesions' thought to represent cystic metastases can be considered as measurable lesions, if they meet the definition of measurability described above. However, if non-cystic lesions are present in the same patient, these are preferred for selection as target lesions.

12.2.2.4 **Target lesions:** All measurable lesions up to a maximum of 2 lesions per organ and 5 lesions in total, representative of all involved organs, should be identified as target lesions and recorded and measured at baseline. Target lesions should be selected on the basis of their size (lesions with the longest diameter), be representative of all involved organs, but in addition should be those that lend themselves to reproducible repeated measurements. It may be the case that, on occasion, the largest lesion does not lend itself to reproducible measurement in which circumstance the next largest lesion that can be measured reproducibly should be selected. A sum of the diameters (longest for non-nodal lesions, short axis for nodal lesions) for all target lesions will be calculated and reported as the baseline sum diameters. If lymph nodes are to be included in the sum, then only the short axis is added into the sum. The baseline sum diameters will be used as reference to further characterize any objective tumor regression in the measurable dimension of the disease.

12.2.2.5 **Non-target lesions:** All other lesions (or sites of disease) including any measurable lesions over and above the 5 target lesions should be identified as non-target lesions and should also be recorded at baseline. Measurements of these lesions are not required, but the presence, absence, or in rare cases unequivocal progression of each should be noted throughout follow-up.

12.2.3 Methods for Evaluation of Measurable Disease

All measurements should be taken and recorded in metric notation using a ruler or calipers.

The same method of assessment and the same technique should be used to characterize each identified and reported lesion at baseline and during follow-up. Imaging-based evaluation is preferred to evaluation by clinical examination unless the lesion(s) being followed cannot be imaged but are assessable by clinical exam.

12.2.3.1 Clinical lesions: Clinical lesions will only be considered measurable when they are superficial (e.g., skin nodules and palpable lymph nodes) and ≥ 10 mm diameter as assessed using calipers (e.g., skin nodules). In the case of skin lesions, documentation by color photography, including a ruler to estimate the size of the lesion, is recommended.

12.2.3.2 Chest x-ray: Lesions on chest x-ray are acceptable as measurable lesions when they are clearly defined and surrounded by aerated lung. However, CT is preferable.

12.2.3.3 Conventional CT and MRI: This guideline has defined measurability of lesions on CT scan based on the assumption that CT slice thickness is 5 mm or less. If CT scans have slice thickness greater than 5 mm, the minimum size for a measurable lesion should be twice the slice thickness. MRI is also acceptable in certain situations (e.g. for body scans). Ideally, the same type of scanner should be used and the image acquisition protocol should be followed as closely as possible to prior scans.

12.2.3.4 PET-CT: At present, the low dose or attenuation correction CT portion of a combined PET-CT is not always of optimal diagnostic CT quality for use with RECIST measurements. However, if the site can document that the CT performed as part of a PET-CT is of identical diagnostic quality to a diagnostic CT (with IV and oral contrast), then the CT portion of the PET-CT can be used for RECIST measurements and can be used interchangeably with conventional CT in accurately measuring cancer lesions over time. Note, however, that the PET portion of the CT introduces additional data which may bias an investigator if it is not routinely or serially performed.

12.2.3.5 Tumor markers: Tumor markers alone cannot be used to assess response. If markers are initially above the upper normal limit, they must normalize for a patient to be considered in complete clinical response.

12.2.3.6 Cytology, Histology: These techniques can be used to differentiate between partial responses (PR) and complete responses (CR) in rare cases (e.g., residual lesions in tumor types, such as germ cell tumors, where known residual benign tumors can remain).

Cytology should be obtained if an effusion appears or worsens during treatment when the measurable tumor has met criteria for response or stable disease.

12.2.3.7 **FDG-PET**: While FDG-PET response assessments need additional study, it is sometimes reasonable to incorporate the use of FDG-PET scanning to complement CT scanning in assessment of progression (particularly possible 'new' disease). New lesions on the basis of FDG-PET imaging can be identified according to the following algorithm:

- a. Negative FDG-PET at baseline, with a positive FDG-PET at follow-up is a sign of PD based on a new lesion.
- b. No FDG-PET at baseline and a positive FDG-PET at follow-up: If the positive FDG-PET at follow-up corresponds to a new site of disease confirmed by CT, this is PD. If the positive FDG-PET at follow-up is not confirmed as a new site of disease on CT, additional follow-up CT scans are needed to determine if there is truly progression occurring at that site (if so, the date of PD will be the date of the initial abnormal FDG-PET scan). If the positive FDG-PET at follow-up corresponds to a pre-existing site of disease on CT that is not progressing on the basis of the anatomic images, this is not PD.

Note: A 'positive' FDG-PET scan lesion means one that is FDG avid with an uptake greater than twice that of the surrounding tissue on the attenuation corrected image.

12.2.4 Response Criteria for Patients with Solid Tumor and Measurable Disease

12.2.4.1 **Evaluation of Target Lesions**

Complete Response (CR):

Disappearance of all target and non-target lesions. Any pathological lymph nodes (whether target or non-target) must have reduction in short axis to <10 mm. If immunocytology is available, no disease must be detected by that methodology. Normalization of urinary catecholamines or other tumor markers if elevated at study enrollment (for patients with neuroblastoma).

Partial Response (PR):

At least a 30% decrease in the sum of the diameters of target lesions, taking as reference the baseline sum diameters

Progressive Disease (PD):

At least a 20% increase in the sum of the diameters of target lesions, taking as reference the smallest sum on study (this includes the baseline sum if that is the smallest on study). In addition to the relative increase of 20%, the sum must also demonstrate an absolute increase of at least 5 mm. (Note: the appearance of one or more new lesions is also considered progressions). Note: in presence of SD or PR in target disease but unequivocal progression in non-target or non-measurable disease, the patient has PD if there is

an overall level of substantial worsening in non-target disease such that the overall tumor burden has increased sufficiently to merit discontinuation of therapy

Stable Disease (SD):

Neither sufficient shrinkage to qualify for PR nor sufficient increase to qualify for PD, taking as reference the smallest sum diameters while on study

12.2.4.2 Evaluation of Non-Target Lesions

Complete Response (CR):

Disappearance of all non-target lesions and normalization of tumor marker level. All lymph nodes must be non-pathological in size (<10 mm short axis)

Note: If tumor markers are initially above the upper normal limit, they must normalize for a patient to be considered in complete clinical response.

Non-CR/Non-PD:

Persistence of one or more non-target lesion(s) and/or maintenance of tumor marker level above the normal limits

Progressive Disease (PD):

Appearance of one or more new lesions and/or *unequivocal progression* of existing non-target lesions. *Unequivocal progression* should not normally trump target lesion status. It must be representative of overall disease status change, not a single lesion increase.

12.2.5 Overall Best Response Assessment

Each patient will be classified according to his “best response” for the purposes of analysis of treatment effect. Best response is determined as outlined in [Section 12.8](#) from a sequence of overall response assessments.

12.3 Biomarker Response Criteria for Patients with MTC

Patients with MTC will use the response criteria outlined above in Section 12.2 to evaluate response and progression. Additional biomarker response data will be collected in patients with tumor markers (CEA and/or calcitonin) 2x ULN at baseline.

Complete Response (CR):

Normalization (\leq ULN) of CEA or calcitonin (CTN) level following treatment, confirmed with a repeat CEA/CTN level at least 4 weeks apart.

Partial Response (PR):

A $\geq 50\%$ decrease in the CEA or CTN level relative to the baseline level, confirmed with a repeat CEA/CTN level at least 4 weeks apart.

Progressive Disease (PD):

A \geq 50% increase in the CEA or CTN relative to the prior value on 2 consecutive measurements at least 4 weeks apart (e.g., if the last prior CTN value was 1,000 pg/ml, consecutive values of 1,500 pg/ml and then 2,250 pg/ml at least 4 weeks later would represent progression). The patient must have been taking XL184 for 4 weeks prior to the first measurements and must have continued to take the drug through the time that the second measurement was drawn.

Stable Disease (SD):

$<50\%$ increase or decrease in CTN or CEA level relative to the baseline level.

12.4 Response Criteria for Patients with Solid Tumors and Evaluable Disease**12.4.1 Evaluable Disease**

The presence of at least one lesion, with no lesion that can be accurately measured in at least one dimension. Such lesions may be evaluable by nuclear medicine techniques, immunocytochemistry techniques, tumor markers or other reliable measures.

12.4.2 Complete Response

Disappearance of all evaluable disease.

12.4.3 Partial response

Partial responses cannot be determined in patients with evaluable disease

12.4.4 Stable Disease (SD)

That which does not qualify as Complete Response (CR), Partial Response (PR), or Progressive Disease.

12.4.5 Progressive Disease

The appearance of one or more new lesions or evidence of laboratory, clinical, or radiographic progression.

12.4.6 Overall Best Response Assessment

Each patient will be classified according to his “best response” for the purposes of analysis of treatment effect. Best response is determined as outlined in [Section 12.8](#) from a sequence of overall response assessments.

12.5 Response Criteria for Neuroblastoma Patients with MIBG Positive Lesions

12.5.1 MIBG Positive Lesions

Patients who have a positive MIBG scan at the start of therapy will be evaluable for MIBG response. The use of ^{123}I for MIBG imaging is recommended for all scans. If the patient has only one MIBG positive lesion and that lesion was radiated, a biopsy must be done at least 28 days after radiation was completed and must show viable neuroblastoma.

12.5.2 The following criteria will be used to report MIBG response by the treating institution:

Complete response: Complete resolution of all MIBG positive lesions

Partial Response: Resolution of at least one MIBG positive lesion, with persistence of other MIBG positive lesions

Stable disease: No change in MIBG scan in number of positive lesions

Progressive disease: Development of new MIBG positive lesions

12.5.3 The response of MIBG lesions will be assessed on central review using the Curie scale¹⁴ as outlined below. Central review responses will be used to assess efficacy for study endpoint. See [Section 8.3.1](#) for details on transferring images to the Imaging Research Center.

NOTE: This scoring should also be done by the treating institution for end of course response assessments.

The body is divided into 9 anatomic sectors for osteomedullary lesions, with a 10th general sector allocated for any extra-osseous lesion visible on MIBG scan. In each region, the lesions are scored as follows. The **absolute extension score** is graded as:

[figure not shown]
0 = no site per segment,

1 = 1 site per segment,

2 = more than one site per segment,

3 = massive involvement (>50% of the segment).

The **absolute score** is obtained by adding the score of all the segments. See diagram of sectors below:

The **relative score** is calculated by dividing the absolute score at each time point by the corresponding pre-treatment absolute score. The relative score of each patient is calculated at each response assessment compared to baseline and classified as below:

1. **Complete response:** all areas of uptake on MIBG scan completely resolved. If morphological evidence of tumor cells in bone marrow biopsy or aspiration is present at enrollment, no tumor cells can be detected by routine morphology on two subsequent bilateral bone marrow aspirates and biopsies done at least 21 days apart to be considered a **Complete Response**.
2. **Partial response:** Relative score ≤ 0.2 (lesions almost disappeared) to ≤ 0.5 (lesions strongly reduced).
3. **Stable disease:** Relative score > 0.5 (lesions weakly but significantly reduced) to 1.0 (lesions not reduced).
4. **Progressive disease:** New lesions on MIBG scan.

12.5.4 Overall Best Response Assessment

Each patient will be classified according to his “best response” for the purposes of analysis of treatment effect. Best response is determined from the sequence of the overall response assessments as described in [Table 5](#) in [Section 12.8](#).

12.6 **Response Criteria for Neuroblastoma Patients with Bone Marrow Involvement**

12.6.1 Bone Marrow Involvement

Bone marrow obtained within 28 days prior to study enrollment with tumor cells seen on routine morphology (not by immunohistochemical staining only) of bilateral aspirate or biopsy on one bone marrow sample.

Bone Marrow responses are determined by H&E Staining of bilateral bone marrow biopsies and aspirates.

Complete Response: No tumor cells detectable by routine morphology on 2 consecutive bilateral bone marrow aspirates and biopsies performed at least 21 days apart. Normalization of urinary catecholamines or other tumor markers if elevated at study enrollment.

Progressive Disease: In patients who enroll with neuroblastoma in bone marrow by morphology have progressive disease if there is a doubling in the amount of tumor in the marrow AND a minimum of 25% tumor in bone marrow by morphology. (For example, a patient entering with 5% tumor in marrow by morphology must increase to $\geq 25\%$ tumor to have progressive disease; a patient entering with 30% tumor must increase to $> 60\%$).

In patients who enroll without evidence of neuroblastoma in bone marrow will be defined as progressive disease if tumor is detected in 2 consecutive bone marrow biopsies or aspirations done at least 21 days apart.

Stable Disease:

Persistence of tumor in bone marrow that does not meet the criteria for either complete response or progressive disease.

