5.2 Criteria for Starting Subsequent Cycles

A cycle may be repeated every 28 days if the patient has at least stable disease, has again met laboratory parameters as defined in the eligibility sections [4.1.8.1- 4.1.8.3](#) and [4.1.8.5](#), and has not experienced study-drug related adverse events warranting permanent discontinuation.

Patients who have a delay in starting subsequent cycles for resolution of toxicity should also have the required observations in [Section 8.1](#) until the start of the next cycle.

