PD	Any	Any	Any	Any	PD
Any	PD	Any	Any	Any	PD
Any	Any	PD	Any	Any	PD
Any	Any	Any	PD	Any	PD
SD	CR/PR/SD	Non-PD	Non-PD	Any	SD
PR	CR/PR	Non-PD	Non-PD	Any	PR
CR/PR	PR	Non-PD	Non-PD	Any	PR
CR	CR	Non-PD	Non-PD	Elevated	PR
CR	CR	CR	CR	Normal	CR

Table 5: Overall Response Evaluation for Neuroblastoma Patients and MIBG Positive Disease Only

If patients are enrolled without disease measurable by CT/MRI, any new or newly identified lesion by CT/MRI that occurs during therapy would be considered progressive disease.

MIBG	CT/MRI	Bone Scan	Bone Marrow	Catechol	Overall
PD	Any	Any	Any	Any	PD
Any	New Lesion	Any	Any	Any	PD
Any	Any	PD	Any	Any	PD
Any	Any	Any	PD	Any	PD
SD	No New Lesion	Non-PD	Non-PD	Any	SD
PR	No New Lesion	Non-PD	Non-PD	Any	PR
CR	No New Lesion	Non-PD	Non-PD	Elevated	PR
CR	No New Lesion	CR	CR	Normal	CR

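### Neuroblastoma marrow progression cannot be scored from a baseline above 50% tumor, so a rising marrow counts as Non-PD and can sit inside an overall PR (Section 12.6.1)

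*Combined protocol and SAP*

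**What the plan says.** Section 12.6.1 defines marrow response for neuroblastoma.

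- **Progression, marrow positive at entry.** Two conditions must both hold: "there is a doubling in the amount of tumor in the marrow AND a minimum of 25% tumor in bone marrow by morphology". The section gives two examples: "a patient entering with 5% tumor in marrow by morphology must increase to" at least 25%, and "a patient entering with 30% tumor must increase to" more than 60%. There is no alternative route, such as an absolute increase, for high baselines.
- **Stable disease.** This is the default category: "Persistence of tumor in bone marrow that does not meet the criteria for either complete response or progressive disease".

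The marrow category then feeds the overall response tables in Section 12.8.1. Both tables give overall PD if the marrow is PD. Their SD rows, and all their PR rows, ask only that the marrow be Non-PD:

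- Table 4 (measurable disease; columns CT/MRI, MIBG, bone scan, marrow, catecholamines, overall) has the row "PR CR/PR Non-PD Non-PD Any PR".
- The other table is headed "Table 5: Overall Response Evaluation for Neuroblastoma Patients and MIBG Positive Disease Only" (columns MIBG, CT/MRI, bone scan, marrow, catecholamines, overall). It has the row "PR No New Lesion Non-PD Non-PD Any PR".

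Section 4.1.8.1 admits children with known marrow metastases if blood counts are met, with no upper limit on percent marrow tumor. Section 5.2 also uses the response category: "A cycle may be repeated every 28 days if the patient has at least stable disease".

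**The concern.** A percentage cannot rise without limit. A rule that asks for a doubling becomes harder to meet as the baseline rises, and past a certain baseline it cannot be met at all. For a child beyond that point, the marrow column has no working PD category. Whatever happens in the marrow short of clearance is recorded as stable, and the overall tables accept it as compatible with SD or PR.

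Any resulting misclassification goes toward a better category, and it concerns the children with the heaviest marrow disease. Section 12.6.2 uses these categories to analyse treatment effect, and antitumor activity is a secondary aim (Section 1.2.1). With at most 41 patients (Section 11.1), one wrongly credited PR would be visible in a descriptive response table.

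**Working it through.** **Inputs.** The progression rule, its two examples and the stable-disease default come from Section 12.6.1. The overall rows come from Tables 4 and 5 in Section 12.8.1. The upper bound of 100 follows from the scale being percent tumor. The reference value is taken as the entry percentage, as in both examples.

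**Step 1: reproduce the plan's figures.** For baseline B, the PD threshold is max(2 × B, 25).

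- B = 5: max(10, 25) = 25. The plan says at least 25%.
- B = 30: max(60, 25) = 60. The plan says more than 60%.

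Both agree, but one example uses ≥ and the other uses >.

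**Step 2: find where the threshold leaves the scale.** If doubling means ≥ 2 × B, PD needs 2B ≤ 100, so B ≤ 50. If it means > 2 × B, PD needs 2B < 100, so B < 50.

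| Baseline | 2 × baseline | Reachable if ≥ | Reachable if > |
|---|---|---|---|
| 40% | 80% | yes | yes |
| 49% | 98% | yes | yes |
| 50% | 100% | only at 100% | no |
| 51% | 102% | no | no |
| 55% | 110% | no | no |
| 60% | 120% | no | no |
| 75% | 150% | no | no |

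Above 50% PD is unreachable on either reading. Exactly 50% is a boundary case that depends on which inequality applies.

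**Step 3: carry two children through the tables.**

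- *Marrow 55% to 95%.* 95 / 55 = 1.73, below 2, so the marrow is SD and therefore Non-PD. With MIBG PR, no new CT/MRI lesion and a Non-PD bone scan, Table 5 gives overall PR. With CT/MRI PR, MIBG PR and a Non-PD bone scan, Table 4 also gives overall PR. If CT/MRI is only SD, Table 4 gives SD.
- *Marrow 30% to 61%.* 61 / 30 = 2.03 and 61 ≥ 25, so the marrow is PD and the overall response is PD whatever the other columns show.

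The first child rises by 95 − 55 = 40 points to 95%; the second rises by 61 − 30 = 31 points to 61%. The larger rise, to the higher burden, gets the better category.

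**Step 4: how many could be affected.** In dose escalation, Section 4.1.8.1 requires at least 5 of every 6 patients to be evaluable for hematologic toxicity, and patients with marrow disease are not. That leaves at most 6 − 5 = 1 per cohort of six, of any tumor type. Section 11.1 lifts this restriction for the expansion, but total enrolment is capped at 41. The documents do not say how many patients have neuroblastoma with more than 50% marrow tumor.

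**The case against.** The strongest reply is that the plan tolerates increases short of progression everywhere: marrow rises short of a doubling at any baseline, RECIST growth below 20% or 5 mm, and central-review MIBG change without new lesions. Scoring a modest marrow rise as stable is the design. This stands. Nothing in the documents shows that 55% to 60% is progression. The defect is only that, above 50%, no rise of any size can count.

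Second, the route to an overall PR is narrow. It needs a response on MIBG or CT/MRI, a bone scan that is not PD and no new lesion. On central review, MIBG CR requires a cleared marrow if the marrow was positive at entry (Section 12.5.3), so the route runs through MIBG PR, a relative score of 0.5 or less. Table 3 also requires a second PR assessment for a best response of PR. Such discordance between MIBG and marrow is possible but should be uncommon. This limits the frequency; it does not repair the rule.

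Third, a reader might infer that the rule lets these children stay on treatment. The documents do not support that as a simple consequence. Section 5.2 also requires the laboratory parameters to be met again. Section 10.1 allows removal for clinical or serum-marker progression, or on the physician's judgment. None of these changes the marrow category, but they mean it does not settle continuation alone.

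Fourth, any not-evaluable label creates a step at 50%. A child going from 55% to 56% with MIBG PR would lose the PR, while a child going from 30% to 60% would keep it under the strict inequality. It could also collide with Section 5.2, because not evaluable is not plainly stable disease. Both points are fair, and they limit what the fix may do.

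**Conclusion.** The concern holds as a minor wording defect. For baselines above 50%, marrow PD is arithmetically unreachable, any rise defaults to SD, and Tables 4 and 5 accept that as Non-PD for an overall SD or PR. A reader might extend this to 50% or more. The documents do not support that without qualification, because 50% to 100% is a doubling and only the strict sign in one example excludes it.

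The effect runs in one direction but is small. Response is secondary and Section 11.5 calls its analysis descriptive and exploratory. Few patients are likely to be affected, and PD can still be called on CT/MRI, MIBG, bone scan or clinical grounds. A reader might also infer that the activity results as a whole are biased or that the dose finding is affected. The documents support neither: the number affected is not given, and the MTD, DLT, pharmacokinetic and sample-size provisions do not use the marrow category.

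The conclusion rests on the entry value as reference. Section 12.8.1 refers to the smallest measurement since the start of treatment. If that applied to marrow, the gap would concern children whose lowest recorded value stays above 50%; a child who only rises from entry is in the same position either way.

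**What to change.** In Section 12.6.1:

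- State whether doubling means ≥ or >, and make the two examples agree.
- State that the criterion cannot be met from a baseline above 50%.
- For response reporting only: when baseline is above 50% and the current percentage is above baseline, do not credit the marrow as Non-PD. Report it as not evaluable for progression, and report overall response as not evaluable unless another site gives PD.
- List these patients separately, with baseline and current percentages, so that readers can judge each case.

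Tables 4 and 5 each need one matching row. Table 3 has no entry for a not-evaluable assessment, so the text should say how one enters best response.

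The label should not decide treatment continuation. The sponsor should reconcile Section 12.6.1 with the stable-disease condition in Section 5.2 and with Section 10.1; this review proposes no clinical rule.

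The cost is a few sentences and two table rows. The downside is that a few assessments become not evaluable, including small rises that may only reflect sampling variation, and the treatment of rises changes abruptly at 50%. The separate listing keeps those cases visible.
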